Introduction. Malnutrition is recognized as a major concern by healthcare providers, as well as by patients, families, and caregivers. In a very recent survey, 28% of 1,035 patients, families and caregivers reported that malnutrition was a very significant problem, while 55% reported it was a somewhat significant problem in older adults 65 and older.²⁶ This response aligns with reports that up to 65% of older adults admitted to the hospital are malnourished (National Resource Center on Nutrition, Physical Activity, and Aging, 2015). Thus, it is essential to establish systematic malnutrition screening in the clinical setting and to develop intervention models and standards of nutritional care. The objective of this aim is to investigate the feasibility, fidelity and acceptability of a nutrition intervention protocol providing higher protein intakes before and after surgery in malnourished Veterans. To achieve the objective of this aim, we will test our working hypotheses that recruitment in clinic will have a high yield and that intervention fidelity (adherence, retention) and acceptability (attrition, patient satisfaction) will be predominantly satisfactory. The rationale for this aim is that successful completion of the proposed research will provide necessary knowledge to begin to identify feasible and acceptable interventions for community-dwelling Veterans who are preparing for surgical procedures. When the proposed studies for Aim 1.1 have been completed, it is our expectation that $\geq 75\%$ of patients approached for recruitment will agree to participate, $\geq 75\%$ of the time patients will adhere to the intervention, $\geq 80\%$ of the participants will remain in the study, and that $\geq 80\%$ of participants will find the intervention to be acceptable. Such findings would be of considerable importance, providing a patient-centered viewpoint that will inform the development of nutrition interventions that meet the standards and needs of high-risk Veteran Populations.

Specific Aim 1.2 – *To determine the effect size for planned future studies of enhanced protein supplementation in malnourished Veterans, with physical function as the primary outcome of interest. Of secondary interest are: biomarkers of inflammation (albumin, hsCRP, TNF- α , IL-6), dietary intake, hospital readmission, discharge location, length of skilled care, and ED admission, and physical activity.*

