Setting: The POSH Clinic is an interdisciplinary collaboration between surgery, anesthesiology, geriatrics, nursing, and physical therapy to provide perioperative surgical care for high-risk Veterans at the Durham VAMC. The clinic opens with a conference to review patients to be seen that day. The surgery chief resident presents and the team covers technical issues with the surgery and selection of anesthesia, as well as covering a list of specific care points. The POSH clinic estimates 200 – 400 patients enrolled annually.

VAPOSH Veterans who are malnourished or at risk of being malnourished will be randomly assigned on a 1:1 ratio by computer-generated random numbers to either an education (nutritional counseling) control (PoshControl) arm or high-protein perihabilitation (PeriHab) arm. All will receive nutrition education. Participants in the PeriHab arm will also be provided with high quality protein supplements that will bring their protein intakes to at least 30 grams for each of the 3 meals per day.

Study Arms:

- PoshControl; n = 42: During their VAPOSH clinic visit, participants will be provided nutrition counseling and prescribed to consume protein at 1.0 g/kg of body weight in the form of educational handouts explained by a Registered Dietitian. Participants will also be instructed to consume 1 oral nutrition supplement per day two weeks before surgery.
- PeriHab; n = 42: PeriHab will be provided nutrition counseling and prescribed to consume protein at 1.6 g/kg of body weight) as well as provided 30 g of high quality protein to some 3 times per day for 2 weeks before and 4 weeks after surgery.

Measurements:

After the participant has been consented and HIPAA Authorization forms have been signed, a Registered Dietitian will administer the NRS-2002 screening tool, the PG-SGA, and nutrition focused physical exam. A patient screening “nourished” on the NRS-2002, PG-SGA, and nutrition focused physical exam will not be included in the study. For study candidates who are malnourished or at nutritional risk we will then proceed with baseline assessments (described below). Upon the completion of all baseline assessments, the participant will be randomized to PeriHab or PoshControl. The following variables will be blocked in this order: 1) surgery type and 2) American Society of Anesthesiology (ASA) Physical Status Classification System (≥ 3 versus < 3). An equal number of participants will be randomized across the two arms.

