This study will utilize a Request for HIPPA waiver of Authorization and waiver or alteration of informed consent process to identify potential participants for this research study. This study will be conducted in the context of the POSH clinic and will only include patients who participate in the POSH clinic. Identification of POSH patients: patients scheduled to be seen in general surgery clinic will be screened for candidacy for a POSH referral through CPRS. Specific referral criteria are based on established risk factors for post-operative complications and include age ≥ 60 , multiple comorbid conditions, falls, mobility limitation or documented functional impairment. In addition to an alert being sent to the surgical team, a notice will be sent to the PCP, with information about the program and an invitation to contact the program manager with any questions or additional information. Patients will receive a single appointment to see the POSH team.

Once patients are referred to the POSH clinic, the POSH clinic coordinator, will contact the study staff. At that time, a chart review will be conducted to assess initial eligibility (abdominal surgery, surgery date is at least two weeks after to POSH clinic visit). Potential participants identified will then be sent an introductory letter signed by the PI that describes the study and informs them that they will be called regarding participation. In the letter, potential participants will be given an "opt-out" number to call in order to decline participation and/or further contact regarding participation. Five business days after the mailing, Veterans who have not called the study number to decline participation will be called by a study staff member to request their participation in the research study (see telephone screen script). In the telephone contact, the study staff member will inform the Veteran that he/she was selected for recruitment because he/she is an older Veteran who is been seen at the POSH Clinic and is having abdominal surgery and may be at nutritional risk.

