Data management and quality control: We will employ REDCap (Research Electronic Data Capture) for data entry. Key components of this activity include data entry screen programming and database testing and validation. The database will include study default parameters and ranges for database, protocols, users, and access rights. Access and data entry to the database will be controlled by login permissions, and the database will be backed up daily, with full backups occurring weekly, and quarterly backups retained for perpetuity. The database will be routinely checked for data integrity and quality. In addition, since some data will require direct download from computerized databases (e.g. VA patient information, lab findings) a final relational database will be built to be used for analysis in SAS, combining data from all data sources. This process will include quality control, developing an appropriate query, validation, and justification procedures, auditing, developing a manual of procedures and documentation, interim reporting of data flow, and maintaining security and patient confidentiality of the data base. The analysis database derived from this source data will be de-identified. Identifying information will be viewed and managed only by the data manager and appropriately consented data collection staff.

Quality control procedures will be established for each component of the study. At each level of data management, and for each subject contact, strict adherence to VHA policy will be observed regarding HIPAA, IRB and other VHA patient quality controls. These procedures include not identifying any patient or provider on any of the reports generated from this study. All computer files will be password protected. Files containing names and addresses will have a separate password, will be accessible only to personnel who need to contact the subjects, and will be stored separately. Ultimately, a de-identified file appropriate for analysis will be produced for report generation and analysis. All analysis and Data management personnel are current with all VA mandated security training.

Aim 2.1 Analysis Plan:

Feasibility proportions for future screening and recruitment will be calculated at the end of the intervention using the following:

1. Proportion of patients recruited will be calculated as the number of patients deemed potentially eligible and contacted for enrollment divided by the total number of patients enrolled.

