 - Feasibility Hypothesis: $\geq 75\%$ of patients approached for recruitment will agree to participate

Fidelity proportions will be calculated for adherence and retention at the end of the intervention using the following:

1. Proportion adherent to nutrition intervention will be computed by the number of empty supplement containers divided by the number of possible supplement containers that could be consumed.

2. Proportion adherent to nutrition intervention will also be computed by the number of meals consumed that are 25 grams of protein divided by the number of possible meals that could be achieved. For the PoshControl arm, adherence will be assessed by the number of dietary changes they make based on the educational handout provided to them at baseline. These will be determined by using diet records for 3 days prior to surgery and 3 days following surgery. Diet food records are valid method for collecting dietary intake data and have been administered in Veteran populations.⁴² We have experience administering and analyzing this data.¹

- Adherence Hypothesis: $\geq 75\%$ of the time PeriHab participants will adhere to the intervention and $\geq 75\%$ of the time controls will show at least one recommended dietary change in their 3-day diet record

3. Proportion retention will be computed by dividing the number of retained subjects at the end of the intervention by the total number randomized into the study.

- Retention Hypothesis: $\geq 80\%$ of participants will remain in the study for the duration of the trial

We will calculate these rates of retention and adherence and their respective confidence intervals overall and by group. While non-powerful, we will assess if these rates differ by chi-square test of proportion and Poisson regression respectively. In a series of sensitivity tests, we will assess if adherence overall was impacted by demographic or symptomatic variables (such as chronic health conditions, living arrangements, surgery, functional status, and nutrition status).

Acceptability will be assessed by:

1. Calculating levels of attrition.

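### The 75% recruitment hypothesis is about agreement, but its formula counts patients enrolled, a term the plan does not define and which may exclude willing patients screened out after consent

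*Combined protocol and SAP*

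**What the plan says.** The introduction to Specific Aim 1.1 and the Aim 2.1 Analysis Plan both set the same feasibility hypothesis: at least 75% "of patients approached for recruitment will agree to participate". The only formula given for it, in item 1 of the feasibility proportions in the Aim 2.1 Analysis Plan, is "the number of patients deemed potentially eligible and contacted for enrollment divided by the total number of patients enrolled".

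The order of events comes from three other places.

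- **Before contact.** Under Subject Recruitment, "a chart review will be conducted to assess initial eligibility (abdominal surgery, surgery date is at least two weeks after to POSH clinic visit"). Nutritional status and cognition are not named as part of this step.
- **Contact.** A letter with an opt-out number goes out first. Five business days later, "Veterans who have not called the study number to decline participation will be called by a study staff member to request their participation".
- **After consent.** Under Measurements: "After the participant has been consented and HIPAA Authorization forms have been signed, a Registered Dietitian will administer the NRS-2002 screening tool", followed by the PG-SGA and the physical exam. A patient who screens nourished "on the NRS-2002, PG-SGA, and nutrition focused physical exam will not be included in the study". Cognition, which forms part of an exclusion criterion in Table 2, is listed as a T1 measure, and no study procedure may start before written consent.

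**The concern.** The hypothesis asks how many of those approached are willing. The formula relates those contacted to those enrolled, and the number who agreed does not appear in it. Because eligibility is completed only after consent, a patient can be contacted, agree, sign the form and still not enter the trial. If that patient is not counted as enrolled, the ratio treats a willing person like a refuser, and it mixes willingness with the share of patients at nutritional risk.

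A second ambiguity works in the opposite direction. Veterans who decline in reply to the letter are never telephoned. If the denominator is built from calls, their refusals vanish and the yield looks better than it is.

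Recruitment is the first feasibility result of the pilot, and the plan says these proportions are meant for planning future screening and recruitment. A larger trial needs willingness and eligible share as two separate figures. One blended ratio gives neither.

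**Working it through.** The 75% target is stated as an expectation without a derivation, so there is no figure of the plan's own to reproduce. The check is arithmetic on the formula.

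**Step 1: the order of the ratio, set aside.** As printed, the ratio is contacted/enrolled. Those enrolled are a subset of those contacted, so it cannot fall below 100%: with 84 enrolled, 112 contacted gives 112/84 = 133%, and 336 contacted gives 336/84 = 400%. That is a separate error. From here on the ratio is taken as enrolled/contacted.

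**Step 2: split the ratio.** Let *a* = consented/contacted (agreement) and *e* = eligible/consented (share who pass the post-consent screen).

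- If enrolled means included after the screen: enrolled/contacted = *a* × *e*.
- If enrolled means consented: enrolled/contacted = *a*, which is agreement itself.

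**Step 3: size under the first meaning.** Agreement needed to reach the target is 0.75/*e*. All values of *e* are assumptions.

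| Eligible share *e* | Ratio when agreement is 75% (0.75 × *e*) | Ratio when everyone agrees | Agreement needed for 75% |
|---|---|---|---|
| 0.65 | 48.8% | 65% | not attainable |
| 0.75 | 56.3% | 75% | 100% |
| 0.80 | 60.0% | 80% | 93.8% |
| 0.90 | 67.5% | 90% | 83.3% |
| 1.00 | 75.0% | 100% | 75% |

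In counts, for 84 included with *e* = 0.80 and *a* = 0.75: 84/0.80 = 105 consented and 105/0.75 = 140 contacted. Agreement is 105/140 = 75%, exactly on target, while included/contacted is 84/140 = 60%.

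**Step 4: opt-outs.** Let *o* be the share of letter recipients who opt out. Agreement among all sent the letter is (1 − *o*) × agreement among those called. Assume 100 letters, 15 opt-outs and 80% agreement among the 85 called: 85 × 0.80 = 68 agree. Then 68/85 = 80% of those called, but 68/100 = 68% of those sent the letter. Taking those included after the screen instead, with *e* = 0.80, gives 68 × 0.80 = 54.4, or about 54% of those sent the letter. The inputs are illustrative; the example shows only that one cohort yields three different answers, depending on a choice the plan does not make.

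**The case against.** **Enrolled may simply mean consented.** Table 2 is followed by a statement that individuals will be screened and consented until the sample size of 84 is met. The same analysis plan also says *randomized* when it defines retention, which suggests that *enrolled* is something earlier. On that reading the eligibility effect is nil. This stands as a possible reading. Against it, Study Interventions speaks of enrollees as people in the two arms, and 84 is the sum of two arms of 42, so 84 consents would suffice only if nobody screened out. The Design section uses the word in a third way, enrolling until 84 have completed. The documents do not settle it.

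**The target may be thought unreachable.** A reader might infer this from the statement that "up to 65% of older adults admitted to the hospital are malnourished", which as an eligible share would cap the ratio at 65%. The documents do not support that inference. The figure is an upper value for malnutrition in hospital inpatients. This trial also admits patients at nutritional risk, from a clinic that selects for comorbidity, falls and functional impairment. The Measurements text can also be read as excluding only those who screen nourished on all three tools. The eligible share could well be higher, and no figure is given for this clinic.

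**The letter may already count as contact.** Recipients are invited to decline participation or further contact, which suggests that the letter is a first contact and that opt-outs are in the denominator. That is reasonable, but it is not stated.

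**Yield is a legitimate measure.** Specific Aim 1.1 expects a high recruitment yield, and enrolled/contacted with screen failures included is useful for planning. This stands, and is a reason to report it. It is not a reason to judge an agreement hypothesis by it.

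**One rewrite would cure this and the inverted order.** It can, but reversing the order alone leaves the numerator undefined.

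**Conclusion.** The concern holds in a conditional form. It is certain from the text that the hypothesis is about agreement, that its formula does not contain agreement, and that nutritional screening follows consent. The size depends on two things the documents leave open: whether enrolled means included after screening, and what share of consenters is eligible. If it does mean that, agreement must reach about 94% at an 80% eligible share, or 83% at 90%, before the ratio shows 75%. If enrolled means consented, that effect is zero and only the opt-out question remains.

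Two stronger conclusions should not be drawn. The formula as printed does not make the target unreachable; because of its order, it makes the target impossible to miss. Nor can the corrected ratio be called unreachable, since that needs an eligible share below 75%, for which the documents give no applicable evidence.

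**What to change.** Replace item 1 of the feasibility proportions as follows.

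- Test the 75% hypothesis on patients who sign consent divided by all chart-eligible patients sent the letter, with letter opt-outs counted as refusals.
- Report separately the share of consented patients who meet the nutritional and cognitive criteria, and the share of approached patients who are randomized.
- Define *approached* and *enrolled* once, and use them consistently in the aims, the Design section and the analysis plan.

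The cost is a change of wording and counts from a screening log: letters sent, opt-outs, consents, screen failures and randomizations. Patient procedures do not change. The stated yield may come out slightly less favourable, because refusals by opt-out are counted.

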Introduction. Older adults have reduced adaptive and regenerative capacities to recovery from a surgical insult.²⁷ Thus, when coupled with insufficient energy intake, malnutrition becomes the driver that leads to further deterioration of functional abilities, reduction in lean muscle mass, and inability to maintain physical reserve. A generous and balanced intake of high quality protein (~30 grams) is essential for achieving optimal protein synthesis in older adults²⁸ and is linked to lean mass retention.²⁹ The essential amino acids

found in complete (animal) proteins stimulate translation initiation of the mTOR signaling pathway and increase muscle protein synthesis in older individuals.²⁹ The objective of this aim is to research the effects of a meal-based protein enhanced perihabilitation intervention in malnourished older Veterans undergoing elective surgery on the primary outcome physical function and secondary outcomes, inflammatory biomarkers (albumin, hsCRP, TNF- α , IL-6), dietary intake, hospital readmission, discharge location, length of skilled care, and ED admission, and physical activity. To achieve the objective of this aim, we will test the working hypothesis that Veterans consuming the enhanced protein supplementation will have superior improvements in function compared to the control arm. Approach: We will further refine our working hypothesis in a two-armed pilot trial comparing a high protein nutrition supplement for two weeks pre and post-surgery to an education control arm. We will assess physical function (SPPB) and secondary outcomes two weeks before, the day of surgery, and four weeks post-surgery. The successful completion of the proposed research will provide preliminary data to test this hypothesis in a large scale randomized controlled trial. When the proposed studies for Aim 1.2 have been completed, it is our expectation that the protein intervention will prove to provide higher functional and physiological benefits relative to the control treatment, illustrating the importance of nutritional perihabilitation prior and following surgery in high-risk, vulnerable populations.

Design

[figure not shown]
This is a Randomized Controlled Study. Veterans will be enrolled until 84 participants have completed the study.

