Any Veteran who contacts or is contacted by study staff will be told that their participation is voluntary, and they may choose not to answer any questions that they find too sensitive. Also, Veterans will be told that their participation will not affect their care at the VA. The study staff member will explain the study in detail, including compensation. No study procedures will begin until formal, written informed consent has been obtained.

Consent Process

On the day of their POSH clinic visit, potential participants identified we will be informed again that he or she is being recruited because he/she is having abdominal elective surgery and is a patient in the POSH clinic. The participant will be told that their participation is voluntary, and they may choose not to answer any questions that they find too sensitive. Also, Veterans will be told that their participation will not affect their care at the VA. The study staff member will explain the study in detail. The participant will be given as long as they need to read through the consent form and HIPAA Authorization. Study staff will answer all questions and concerns. No study procedures will begin until formal, written informed consent has been obtained.

Study Interventions

Caloric Intake and Monitoring Protocol for Both Arms: Caloric needs will be prescribed for each participant using an established standard of 30 to 35 kcal/kg⁴¹ at the VAPOSH clinic. To assure adequacy for all enrollees, calculated protein needs will be higher than the recommended 0.8 g/kg of body weight for both arms, **PoshControl** protein prescription = **1.0 g/kg of bodyweight** and **PeriHab** protein prescription = **1.6 g/kg of bodyweight**. Participants will be monitored by weekly phone calls during which study staff will ask the participant to recall their intake from the day before (24-hour dietary recall). This information will be used to ensure that both arms are meeting their calorie needs. If a participant in either arm has an inadequate intake they will be counseled on how to increase their current intake. Based on our previous assessment of similar populations, it is unlikely that the **PeriHab** arm will be able to meet the 1.6 g/kg of body weight protein prescription on their own and for that reason we are providing protein supplement to be consumed 3 times a day (as described below). The **PoshControl** arm will be given one ONS to consume every day prior to surgery.

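### The recruitment proportion is defined upside down (contacted ÷ enrolled), so its own 75% target would be met at any uptake

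*Combined protocol and SAP*

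**What the plan says.** In Data Analysis and Statistical Considerations, Aim 2.1 Analysis Plan, feasibility item 1 sets the proportion of patients recruited equal to the "number of patients deemed potentially eligible and contacted for enrollment divided by the total number of patients enrolled". The feasibility hypothesis attached to that item is that at least 75% "of patients approached for recruitment will agree to participate". The introduction to Specific Aim 1.1 gives the same target in the same terms and presents it as an expectation ("it is our expectation that").

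The route into the study is set out in three places:

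- **Subject Recruitment.** After chart review, "Potential participants identified will then be sent an introductory letter signed by the PI". The letter carries an opt-out number. Those who have not declined after five business days "will be called by a study staff member to request their participation in the research study".
- **Consent Process.** At the clinic visit the patient "will be informed again that he or she is being recruited", and "No study procedures will begin until formal, written informed consent has been obtained".
- **Design, under Measurements.** The nutrition screen and examination follow consent. Patients found to be nourished are left out, and the rest are randomised after baseline assessments.

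On accrual, the Design section says "Veterans will be enrolled until 84 participants have completed the study".

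**The concern.** The formula and the hypothesis cannot describe the same quantity. One puts contacted patients in the numerator; the other puts approached patients in the denominator.

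Feasibility is named in the Purpose and comes first in Specific Aim 1.1. The plan also says these proportions are for future screening and recruitment, so the figure is meant to inform the larger trial. If the sentence is followed as written, the reported value cannot show poor recruitment. Worse uptake gives a larger number, and a larger number looks better against a target of the form at least 75%.

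**Working it through.** The 75% is a target and not a derived figure, so the plan has no calculation here to reproduce. The check is what the written ratio returns.

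**Inputs**

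- Written ratio: contacted ÷ enrolled (Aim 2.1 Analysis Plan, feasibility item 1).
- Hypothesis: agreeing ÷ approached ≥ 0.75 (the same plan, and Specific Aim 1.1).
- Enrolled patients are a subset of contacted patients (Subject Recruitment and Consent Process).

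**Step 1: the range of the written ratio.** Let p = agreeing ÷ approached, and for this step treat enrolled as agreeing and contacted as approached. The written ratio is then 1/p. For 0 < p ≤ 1, 1/p ≥ 1, which always exceeds 0.75.

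| True uptake p | Written ratio 1/p | Is p ≥ 75%? | Is the written ratio ≥ 75%? |
|---|---|---|---|
| 100% | 100% | yes | yes |
| 75% | 133% | yes | yes |
| 60% | 167% | no | yes |
| 50% | 200% | no | yes |
| 25% | 400% | no | yes |

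**Step 2: the direction of the comparison.** p ≥ 0.75 is equivalent to 1/p ≤ 1/0.75 = 1.333. To test the hypothesis with the written ratio, both the threshold and the inequality would have to change.

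**Step 3: the same result in counts.** Take 84 enrolled. The numbers contacted below are illustrative, since the plan gives none; 400 is the top of the clinic's estimated annual volume.

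| Contacted | Written: contacted ÷ 84 | Reciprocal: 84 ÷ contacted |
|---|---|---|
| 112 | 1.33 | 75% |
| 168 | 2.00 | 50% |
| 400 | 4.76 | 21% |

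**Step 4: is this a house convention?** No. In the same plan, container adherence is empty containers over possible containers, meal adherence is qualifying meals over possible meals, and retention is retained over randomised. Only the recruitment item is inverted, and the correct formula appears nowhere else.

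**Step 5: does a plain swap suffice?** Not fully. Because the nutrition screen follows consent, randomised ÷ approached = (agreement rate) × (share of consenting patients who pass the screen). With agreement at exactly 0.75, any pass share below 1 takes the product below 0.75. The plan gives no pass share. If it were 80%, the product would be 0.75 × 0.80 = 60%; over an assumed range of 50% to 100% it runs from 37.5% to 75%. The numerator therefore needs to be named.

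**The case against.** The strongest case is that the page corrects itself. The hypothesis below the formula states the intended numerator and denominator in words, and a proportion of 133% or 200% would alert any analyst. No decision rule hangs on the figure: the 75% is an expectation, and confidence intervals and between-arm tests are planned only for retention and adherence. This is a fair argument about consequence, and it keeps the point minor. It does not make the formula right, because the formula is the operative definition.

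A second objection is that turning the ratio over still leaves the denominator loose. A patient who opts out after the letter is never called, and the plan does not say whether that patient was approached. This can change the verdict. As an illustration with an assumed count, 84 consents among 112 called is 75.0%; adding 20 earlier opt-outs gives 84/(112 + 20) = 63.6%. This stands, and the corrected sentence should settle it.

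A third objection is that the doubt over the word enrolled is weaker than the inversion itself. The Design section does not place enrolment before or after the nutrition screen, and Selection of Subjects does not settle it either. If enrolled means consented, a plain swap already matches the hypothesis. That is correct, and the one-patient effect at exactly 75% is a boundary case. Naming signed consent still costs nothing and removes the doubt.

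**Conclusion.** The concern holds. The recruitment proportion as written is the reciprocal of the quantity in its own hypothesis. It is never below 100%, it rises as recruitment worsens, and set against at least 75% it gives the wrong verdict for every uptake below 75%.

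The result rests on one premise, taken from the plan's own recruitment steps: nobody enrols without first being contacted. No contact count or screening pass rate is needed for it.

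The severity is minor. The error is most likely a drafting slip, the same counts give the right figure once inverted, and sample size, safety monitoring and the Aim 1.2 analysis are unaffected.

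**What to change.** Replace feasibility item 1 with wording such as:

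*Proportion agreeing = number of potentially eligible patients approached who sign informed consent, divided by the number of potentially eligible patients approached, compared with 75%.*

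Add a clause defining approached. Counting everyone who was sent the letter, including those who opt out, is the natural choice, because the opt-out number is offered as a way to decline participation. Count agreement at signed consent and not at the telephone call, which only requests participation.

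As an optional clarification, report randomised ÷ consented separately as the screening yield, so that willingness to take part and nutritional eligibility are not mixed.

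The cost is one rewritten sentence with its definition, plus one sentence if the yield is reported. It needs counts of patients approached (with opt-outs identified), consented and randomised. Nothing changes in the design, the sample size or the assessments.
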